1.6 Risk analysis

This study is considered to be a non-significant risk study based on United State Food and Drug administration (FDA) and International Standards Organization (ISO) guidelines due to the daily wear nature of the study. With the potential benefit of this study, the work is considered to be ethically justifiable. [REDACTED]

[REDACTED]).
The work where practical will be conducted in accordance with the ICH Good Clinical Practice Guidelines and the international standard BS EN ISO 14155:2011 'Clinical investigation of medical devices for human subjects'.

Section 2. Resources

2.1 Subject selection

In this work up to 30 subjects will be recruited and enrolled.

2.1.1 Subject withdrawal and replacement

This study includes three clinical visits. Once the study consent form is signed, the subject is considered to be enrolled on the study. Subjects who have signed the consent form, but who have not completed the dispensing visit will usually be replaced. All subject data will be included in the final analyses unless there are strong grounds for exclusion; such grounds will be detailed in the final report. At the end the study, all subjects will sign a study exit form.

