1.5 Statistical considerations

The principal hypothesis to be tested in this work is that subjective scores and visual acuity for the lenses will be substantially equivalent.

[REDACTED]

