2.6.1.1 Use of lenses

All lens types will be worn on a daily wear basis. Lenses should be worn for a minimum of six hours per day, five days per week. The lenses should also be worn for a minimum of two hours before attending the follow-up visits.

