3.2.3 Two-week follow-up/dispensing 2 visit

Subjects should attend wearing the study lenses which should have been in situ for at least two hours. Subjects who attend without lenses in situ for at least two hours will usually be rescheduled. The following procedures will be performed:

1. Lens wearing time on study visit day will be recorded.
2. Any study products relating to the previous two weeks of the study will be collected.
3. Details of the contact lens wear since the previous visit will be recorded (including wear time and comfortable wear time).
4. The subject will be asked to score the following with reference to appropriate visual analogue scales (0-100) as outlined in the 'Subjective ratings' document in [REDACTED]
[REDACTED]

[REDACTED]

[REDACTED]

- ∞ Overall comfort
- ∞ Dryness during the day

[REDACTED]

- ∞ Visual fluctuation/stability

[REDACTED]

[REDACTED]

- ∞ Overall handling
- ∞ Overall satisfaction
- ∞ Distance vision
- ∞ Intermediate vision
- ∞ Near vision
- ∞ Near vision in dim illumination

- ∞ Ghosting at distance

- ∞ Ghosting at near

- ∞ [REDACTED]

- ∞ Vision whilst driving during the day

- ∞ Vision whilst driving at night

- ∞ [REDACTED]

[REDACTED]

[REDACTED]

[REDACTED]

[REDACTED]

[REDACTED]

[REDACTED]

[REDACTED]

[REDACTED]

[REDACTED]

[REDACTED]

[REDACTED]

[REDACTED]

[REDACTED]

[REDACTED]

- 6. High illumination, high and low contrast distance and near (40 cm) monocular and binocular visual acuity will be recorded using distance and near logMAR charts before over-refraction. The range of clear vision at near (binocularly) will also be recorded for high contrast measures.
- 7. High illumination, binocular high contrast near visual acuity will be recorded at the subject's habitual working distance (which was recorded at the initial visit) using a near logMAR chart.
- 8. Spherical over-refraction will be performed on each eye if binocular distance high contrast visual acuity is less than 0.2. High illumination, high and low contrast distance and near (40 cm) monocular and binocular visual acuity will be recorded using distance and near logMAR charts. The range of clear vision at near (binocularly) will also be recorded for high contrast measures.

[REDACTED]

[REDACTED]

[REDACTED]

- 11. Lens rotation and stability will be recorded.
- 12. Lens fit and surface will be recorded as described in Section 3.2.1.

[REDACTED]

[REDACTED]

[REDACTED]

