3.3 Monitoring subject compliance

Subjects are required to adhere to the instructions provided during this clinical investigation. This will be confirmed at the study visits by verbal questioning of the subject by the investigator.

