3.4 Missing, unused and spurious data

The absence of any data will be carefully and critically considered. If appropriate, partial datasets will be included in the final analysis. Any data missing from a subject visit will be outlined in the report by indicating the number of subjects included for each analysis. Data that are unused or considered to be spurious will be detailed and discussed in the report.

Section 4. Study co-ordination

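### The visible plan tests equivalence on all subject data and never uses the wear minimum or recorded wear time, so robustness to under-wear cannot be judged

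*Combined protocol and SAP*

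**What the plan says.** **Hypothesis.** Section 1.5: "The principal hypothesis to be tested in this work is that subjective scores and visual acuity for the lenses will be substantially equivalent". The text directly after this sentence is redacted.

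**Analysis set.** Section 2.1.1: "All subject data will be included in the final analyses unless there are strong grounds for exclusion". It adds that "such grounds will be detailed in the final report", but does not say beforehand what they are. Section 3.4 is similarly open: "If appropriate, partial datasets will be included in the final analysis".

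**Wear requirement.** Section 2.6.1.1: "Lenses should be worn for a minimum of six hours per day, five days per week". Willingness to keep to this schedule is also inclusion criterion 11 (section 2.1.3).

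**Wear data.** Section 3.2.3, step 3: "Details of the contact lens wear since the previous visit will be recorded (including wear time and comfortable wear time"). Section 3.3 covers adherence to instructions: "This will be confirmed at the study visits by verbal questioning of the subject by the investigator".

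No visible section connects these wear data to an analysis set, a sensitivity analysis or a planned tabulation.

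**The concern.** When the aim is to show a difference, analysing everyone is the cautious choice. When the aim is to show equivalence, anything that pulls the lens difference towards zero helps the claim, so the all-data analysis is no longer conservative by default.

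The exposed outcomes are the visual analogue scores for comfort, dryness, handling, satisfaction and vision in daily tasks. They are meant to reflect two weeks of use. A subject who wore a lens on only a few short days still gives a full set of scores, perhaps with too little experience to separate the two lenses. Acuity is less exposed, because it is measured with the lens on the eye.

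At stake is how a finding of equivalence is read. On the visible plan, a reader of the final report could not tell whether similar scores came from similar lenses or from lenses that were little used.

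**Working it through.** **1. The plan's own figure.** Section 1.5.1 gives 16 completers for 80% power to detect 10 units (two-sided paired test, alpha 0.05). No SD is stated, so 16 cannot be checked independently. The formula can be solved for the SD of the paired differences instead:

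power = P(|T| > t(0.975, n − 1)), where T is noncentral t with n − 1 degrees of freedom and noncentrality 10·√n / SD.

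Setting power to 0.80 at n = 16 gives SD = 13.34. An SD from about 12.9 to 13.3 would round up to 16 completers, so 13.34 is the top of the range.

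**2. Dilution.** Let f be the share of under-wearers and r the proportion by which their lens difference shrinks. A negative r means it grows. Then

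observed mean difference = true difference × (1 − f·r).

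With a true difference of 10 and f = 0.2:
- r = 0: 10 × (1 − 0) = 10.0
- r = 0.5: 10 × (1 − 0.10) = 9.0
- r = 1: 10 × (1 − 0.20) = 8.0
- r = −0.5: 10 × (1 + 0.10) = 11.0

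**3. Effect on an equivalence conclusion.** No equivalence limit or decision rule is visible. I assume limits of ±10 units (the planning difference) and two one-sided paired t-tests at 5% each. Subjects were simulated as a mixture of wearers and under-wearers, with SD 13.34 and a true difference equal to the limit. The entries are the share of trials that wrongly conclude equivalence at n = 30:

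| Under-wearers | Difference 50% larger | Unchanged | Halved | Vanishes |
|---|---|---|---|---|
| 10% | 3% | 5% | 7–8% | 10% |
| 20% | 2% | 5% | 10% | 19% |
| 30% | 1% | 5% | 15% | 30–31% |

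At 22 completers, the larger of the two requirements in section 1.5.1, the 20% row is 2%, 5%, 9–10% and 16%.

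**4. Extra noise without shrinkage.** If under-wear only makes scores noisier, an equivalence test loses power. With a true difference of zero, n = 30 and 20% of subjects at 1.5 times the SD, the chance of correctly concluding equivalence falls from 98.2% to 94.5%. If equivalence were instead read from a non-significant difference test, the same noise would favour the claim. At a true 10-unit difference the chance of non-significance rises from 2.3% to 5.8%.

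**5. What the documents supply.** They give the wear minimum, the visit window, the in-situ time and the bar on non-study products. They give no expected or observed under-wear rate and no value for r. The table shows how sensitive a conclusion could be; it does not estimate what will happen.

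**The case against.** The strongest objection is about direction. A reader might infer that under-wear dilutes the difference and so makes equivalence easier to claim. The documents do not support that as a general statement. Each subject wears and rates both lenses, so under-wear is not a switch to the comparator. Someone who leaves a lens out because it is uncomfortable or blurs vision may well score it low, which widens the difference. The first column of the table shows that case. This part of the objection stands.

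Other points on that side:

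- **Redaction.** A reader might also infer that the plan contains no per-protocol analysis at all. Section 1.5 is redacted straight after the hypothesis, and a method, limit or analysis set may be there. The point is confined to the visible text.
- **Not strictly all data.** Section 2.1.1 allows exclusions. True, but because the grounds are not fixed, they could be chosen after results are known, in either direction. This adds to the case for defining a compliant set in advance.
- **Existing safeguards.** Subjects must have worn soft lenses successfully and be willing to keep to the schedule (section 2.1.3). Those without two hours of wear at follow-up are usually rescheduled (section 3.2.3). Discontinuation is possible for repeated refusal to follow instructions or use of non-study products (section 2.2). These make heavy under-wear less likely. They do not ensure two weeks of experience, and discontinuation on these grounds is discretionary.
- **Power.** A loss of power to detect a difference is easily overstated. If 10% of subjects contributed no difference, the mean would be 9.0 units. Power would be 71% at 16 completers, but 86% at 22 and 95% at 30.
- **A more basic gap.** Without a visible limit, a rule requiring both analyses to fall inside it cannot be applied. That is why the second analysis is proposed as support and not as a second hurdle.

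**Conclusion.** The point holds in a limited form. For an equivalence hypothesis, the visible plan has one loosely bounded all-data rule and makes no analytic use of the wear minimum or of recorded wear time. Robustness of the subjective-score conclusion to under-wear cannot be judged from it.

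Neither the direction nor the size of any bias is established. With 20% under-wearers and 30 subjects, the illustrative false-equivalence rate runs from about 2% to 19% around a nominal 5%, depending wholly on how under-wearers score. That range rests on an assumed limit of 10 units, an assumed pair of one-sided tests, a back-solved SD and an assumed under-wear share. The point concerns mainly the scores. It is worth acting on because the data are already to be collected and the remedy is useful whichever way the bias runs.

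**What to change.** 1. Keep the all-data analysis as stated.
2. Add a supporting per-protocol analysis, fixed before results by lens are seen. It should use the protocol's existing conditions, met in both periods: six hours a day on five days a week (section 2.6.1.1); follow-up within 10–18 days of dispensing (section 3.1, Table 3); at least two hours of wear before the visit (section 3.2.3); and no non-study lenses or solutions (section 2.2).
3. Tabulate wear time by lens, and the number of subjects below the wear minimum by lens with reasons, so that under-wear caused by a lens shows as a result in itself.
4. State in advance that the equivalence conclusion will be qualified if the two analyses disagree.

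**Cost.** A few sentences, one table and one repeat of the planned analysis on data already collected. The second set will be smaller and may lose subjects who disliked a lens, so it supports the all-data analysis and does not replace it. Wear time is self-reported, so the compliant set will be only as accurate as subjects' answers.

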2.1.2 Subject recruitment

Subjects will be recruited by one or more of following means:

[REDACTED]

[REDACTED]

[REDACTED]

[REDACTED]

[REDACTED]

2.1.3 Inclusion criteria

Subjects will only be eligible for the study if:

1. They are aged 40 - 70 years, inclusive.
2. They understand their rights as a research subject and are willing and able to sign a Statement of Informed Consent.
3. They are willing and able to follow the protocol.
4. They have successfully completed the non-dispensing study (C16-597) as the lenses to be worn on this study (C16-599) are predetermined from their participation on study C16-597.
5. They have a contact lens spherical prescription between +10.00 to -10.00D (inclusive).
6. They have astigmatism between of -0.75 and -5.75DC (based on the calculated ocular refraction) in each eye.
7. They have an Add component to their spectacle refraction (between +0.75 and +2.50DS).
8. They can be satisfactorily fitted with the study lenses.

9. They can attain at least 0.30 logMAR binocular distance high contrast visual acuity with the study lenses within the available power range.
10. They have successfully worn soft contact lenses in the last two years.
11. They are willing to comply with the wear schedule (at least five days per week and for at least six hours per day).
12. They agree not to participate in other clinical research for the duration of this study.
13. They own a wearable pair of spectacles.

2.1.4 Exclusion criteria

Subjects will not be eligible to take part in the study if:

1. They have an ocular disorder which would normally contra-indicate contact lens wear.
2. They have a systemic disorder which would normally contra-indicate contact lens wear.
3. They are using any topical medication such as eye drops or ointment.
4. They have had cataract surgery.
5. They have had corneal refractive surgery.
6. They have any corneal distortion resulting from previous hard or rigid lens wear or have keratoconus.
7. They are pregnant or breast-feeding.
8. They have any clinically meaningful slit lamp findings contraindicating contact lens wear (e.g. \geq Grade 3 finding of oedema, corneal neovascularisation, corneal staining, tarsal abnormalities, conjunctival injection, blepharitis/meibomian gland dysfunction) on the Efron classification scale or any other ocular abnormality that in the opinion of the investigator would contraindicate contact lens wear.
9. They have any infectious disease (e.g. hepatitis) which would, in the opinion of the investigator, contraindicate contact lens wear or pose a risk to study personnel; or they have any immunosuppressive disease (e.g. HIV).
10. They have a history of anaphylaxis or severe allergic reaction.
11. They have taken part in any other contact lens or care solution clinical trial or research, within two weeks prior to starting this study.

2.2 Subject discontinuation

In general, subjects should be discontinued at any time, if it is in their best interests, as judged by the investigator. Reasons for this may include clinical signs of grade 3 or more, lack of motivation, discomfort, repeated refusal to follow instructions or the use of non-study products such as solutions or lenses. Subjects will be discontinued if a serious adverse event occurs or if they miss two or more planned consecutive visits. Subjects who

fail to satisfy all the inclusion and exclusion criteria will be discontinued and replaced. Subjects may choose to leave the study at their own request. All discontinuations will be carefully recorded.

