1.5.1 Power analysis

In order to determine the study sample size, power analysis was employed using subjective vision data from a previous clinical study. In order to achieve 80% power to detect a difference of 10 units for subjective vision (assuming an alpha of 0.05 and two-tailed paired analysis), 16 completing subjects are required. In order to achieve 80% power to detect a difference of half a line on a LogMAR chart (assuming an alpha of 0.05 and two-tailed paired analysis), 22 completing subjects are required. To allow for discontinuations, 30 subjects will be recruited.

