3.2.4 Four week follow-up/exit visit

Subjects should attend wearing the study lenses which should have been in situ for at least two hours. Subjects who attend without lenses in situ for at least two hours will usually be rescheduled.

The same procedures as at the two week follow-up (Section 3.2.3) will be carried out except that no more lenses will be dispensed. The following additional procedures will be carried out:

[REDACTED]

[REDACTED]

[REDACTED]

[REDACTED]

[REDACTED]

[REDACTED]

[REDACTED]

[REDACTED]

[REDACTED]

[REDACTED]

[REDACTED]

[REDACTED]

[REDACTED]

[REDACTED]

[REDACTED]

[REDACTED]

[REDACTED]

[REDACTED]

[REDACTED]

[REDACTED]

[REDACTED]

[REDACTED]

[REDACTED]

[REDACTED]

[REDACTED]

[REDACTED]

[REDACTED]

[REDACTED]

[REDACTED]

[REDACTED]

[REDACTED]

[REDACTED]

6. On the final visit (or when the subject is discontinued at an earlier visit), the subject will sign a study exit statement acknowledging that the work is complete, although they may have been asked by the investigator to attend a post-study follow-up visit, and that they should continue to use their lenses and solutions as advised, and seek aftercare for their contact lenses. A copy of this signed form will be issued to the subject.
7. The subject will be issued with their payment and all study products will be collected.

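### A lens stopped early for discomfort or signs may have no after-wear score; if such stops are unequal between lenses, the comparison can be biased towards equivalence

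*Combined protocol and SAP*

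**What the plan says.** Section 1.5 states the principal hypothesis, that "subjective scores and visual acuity for the lenses will be substantially equivalent". The text after it is redacted, and no equivalence margin is visible. Section 1.5.1 sizes the study for "80% power to detect a difference of 10 units for subjective vision", "assuming an alpha of 0.05 and two-tailed paired analysis", and concludes that "16 completing subjects are required". The acuity target needs 22, and 30 are to be recruited.

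Under Sections 1.4 and 3.1 each lens has one follow-up, after two weeks of wear. Section 3.2.3 collects the 0-100 ratings there (step 4, including comfort and satisfaction), then acuity (step 6), with the slit lamp examination at step 19. High-contrast acuity with the lenses is also taken at dispensing (Section 3.2.2, steps 20 to 22), but only after a short settling period.

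On stopping early, Section 2.2 says: "Reasons for this may include clinical signs of grade 3 or more, lack of motivation, discomfort, repeated refusal to follow instructions". It adds that discontinuations are recorded. Section 3.2.4 has the exit statement signed at the last visit or "when the subject is discontinued at an earlier visit". The visible text does not ask for ratings or acuity at that point, although other steps in that section are redacted.

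On missing data, Section 2.1.1 keeps every subject's data by default, with any exclusion justified in the report. Section 3.4 says: "If appropriate, partial datasets will be included in the final analysis", and the number of subjects in each analysis is to be given. Section 3.1.1 has data from unscheduled visits recorded, without a visible rule for using them.

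**The concern.** Discomfort is both a reason to stop and close to a scored outcome. A subject who cannot tolerate a lens and leaves before its follow-up is likely to be one who would have rated it poorly, yet the scheduled visit that would capture the rating never happens. The within-subject comparison then rests on subjects who tolerated both lenses.

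For a superiority claim, losing such subjects would tend to cost the sponsor a finding. Here the hypothesis is similarity, so shrinking a real difference favours it. A lens that a minority cannot wear could look equivalent because that minority is missing on the lens that failed. A rating not taken when the subject leaves cannot be obtained later.

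**Working it through.** **1. Who lacks a score.** Setting Section 2.2 against the visit order in Section 3.2.3:

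| When the subject stops | Score on the stopped lens | Score on the other lens | Pair |
|---|---|---|---|
| Lens 1, before its follow-up | none, unless scored at an unscheduled visit | none, never worn | no |
| Lens 1, for signs found at its follow-up | yes (steps 4 and 6 precede step 19) | none, never worn | no |
| Lens 2, before its follow-up | none, unless scored at an unscheduled visit | yes | no |
| Lens 2, for signs found at its follow-up | yes | yes | yes |

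The concern applies to the first and third rows. In the third, a mixed model can use the score on the tolerated lens but still has none for the stopped one.

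**2. The plan's own figure.** Section 1.5.1 gives no SD, so 16 cannot be reproduced independently, only inverted. For a two-sided paired t-test (noncentral t, n − 1 degrees of freedom), 80% power at 10 units first needs n = 16 when the SD of the paired differences is about 12.9 to 13.3. The normal approximation, SD = 10 × √16 / (1.96 + 0.84), gives 14.3. I use 13.1.

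**3. The allowance for loss.** 30 − 22 = 8 subjects, or 8/30 = 26.7%, can be lost with both power targets still met, since 22 / (1 − 8/30) = 30. Reaching the planned number of completers is therefore no safeguard against selective loss.

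**4. Size, one-sided stopping.** Assumptions, none from the documents: the mean difference is 5 units in subjects who tolerate both lenses; k of 30 stop the same lens and would have differed by d units in the same direction; SD is 13.1; the margin is ±10 units (borrowed from the sizing difference), judged by a 90% confidence interval. The all-subject mean is [(30 − k) × 5 + k × d] / 30. The probabilities are simulated (100,000 trials).

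| k | d | All-subject mean | Chance CI within ±10, completers | Same, all 30 scored |
|---|---|---|---|---|
| 2 | 15 | (140 + 30)/30 = 5.7 | 63% | 54% |
| 2 | 20 | (140 + 40)/30 = 6.0 | 63% | 47% |
| 2 | 30 | (140 + 60)/30 = 6.7 | 63% | 32% |
| 4 | 20 | (130 + 80)/30 = 7.0 | 60% | 29% |
| 4 | 30 | (130 + 120)/30 = 8.3 | 60% | 10% |

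The completer mean is 5.0 throughout. Letting all 8 spare subjects fail one lens at 30 units gives (110 + 240)/30 = 11.7 and 53% against 0.2%. That is an extreme case.

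**5. Size, balanced stopping.** With 4 stops, two on each lens at +30 and −30, the all-subject mean is (130 + 60 − 60)/30 = 4.3 against 5.0 in completers. The completer mean now overstates the difference.

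**6. A milder mechanism.** In a second simulation a pair is lost when either lens's score falls below a tolerance threshold (assumed: SD of differences 13.4, between-subject SD 10, control mean 75, thresholds 45 to 55). A true difference of −10 becomes −9.2 to −8.2 with 8 to 26% of pairs lost. A true −5 becomes −4.7 to −4.3 with 5 to 18% lost. A true 0 stays 0. The attenuation is about 0.3 to 1.8 units.

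**The case against.** A reader might infer that the plan prescribes a completers-only analysis. It does not. The phrase about completing subjects is sizing language in Section 1.5.1, and Sections 2.1.1 and 3.4 lean towards including what data there are. This stands, but inclusion rules act only on data that exist and cannot supply a rating nobody took.

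A reader might also infer that every discontinuation for grade 3 signs loses the failing lens's score. The visit order says otherwise: signs found at the follow-up slit lamp come after the ratings and acuity, and a one-period mixed model could use those data. Subjects who attend early are examined and their data recorded (Section 3.1.1), and follow-up is allowed from day 10 (Section 3.1). The gap is confined to stops before follow-up without scoring. For acuity it is softened a little by the dispensing measurement, though that does not reflect two weeks of wear.

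Many stops may have nothing to do with the lens, since Section 2.2 also lists motivation, instructions and non-study products. Entry requires completion of an earlier non-dispensing study, a satisfactory fit and recent successful soft lens wear (Section 2.1.3), so widespread intolerance is unlikely. Finally, redactions in Sections 1.5 and 3.2.4 may hide an analysis rule or an exit-scoring step. These points limit the size and certainty of the concern; they do not close the gap in the visible text.

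**Conclusion.** The point holds in a conditional form. On the visible text, a subject who stops a lens before its follow-up and is not scored at an unscheduled visit leaves no after-wear score for that lens and no pair, and no stated inclusion rule repairs this. If such stops are commoner on the worse-scoring lens, the result can be biased towards equivalence.

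The stronger statement, that the trial is biased towards its hypothesis, is not supported. It needs unequal stopping, and the documents give no discontinuation rate by lens. Balanced stopping gives no bias when the lenses are truly equal, and can give bias the other way when they are not.

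The size cannot be fixed from the documents. With 2 to 4 of 30 stopping one lens at differences of 15 to 30 units, the understatement is 0.7 to 3.3 units (5.7 − 5.0 to 8.3 − 5.0), and the chance of meeting an assumed ±10 margin is 54% down to 10%, against 60 to 63% in completers. Under the milder threshold mechanism the attenuation is only 0.3 to 1.8 units. The change is worth making because it is cheap and the scores cannot be recovered afterwards.

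**What to change.** Leave the discontinuation rule as it is, and make three additions.

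1. In Sections 2.2 and 3.2.4: when a subject stops during a lens period, record the Section 3.2.3 ratings for that lens, and acuity if the lenses are in, at the discontinuation or unscheduled contact. State that these values serve as that lens's outcome.
2. In Section 3.4: report the number of lens-related discontinuations for each lens beside the lens comparison.
3. As a supportive sensitivity analysis, repeat the comparison in all dispensed subjects, giving an unfavourable score (for example the worst observed) to any lens stopped for a lens-related reason and not scored. This should inform interpretation, not act as a second condition for the equivalence claim, because worst-score imputation is only one conservative choice among several.

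If the redacted text already covers any of these, a cross-reference is enough. The cost is protocol wording, a few minutes of scoring per discontinuing subject at a contact that may already take place for the exit statement, and one extra analysis. The drawback is that some scores will reflect less than two weeks of wear, so they should be flagged. If nobody stops for a lens-related reason, the result does not change.
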